T2.3 Comparing rates, types, severity of irAEs between ePRO follow up and standard of care	D2.3 Statistical analyses of differences between groups
T2.4 Write article about findings	D2.4 Published article

WP3: Influence on QoL and OS of ePRO follow-up as standard of care

Target: WP3 is based on H3 with the aim to reach O3

Method: An ambi- directional multicentre cohort study	
Description of activities: 300 patients receiving immunotherapy and followed by ePRO during 2024-2025 from NLSH and HSYK will be included in a prospective arm. These will be compared to a retrospective cohort of 600 patients from WP1 including patients from UNN and HSYK with standard follow-up who received immunotherapy during the years 2020-2023, and matched on cancer diagnosis. HRQoL will be measured using EORTC QLQ-C30 version 3.0(18,19) included in the ePRO module. Overall survival will be compared using Kaplan Meier analysis.	
Tasks	Deliverables
T3.1 Data collection and randomisation	D3.1 Data set of study population with low selection bias
T3.2 Report on new knowledge on reduction of severe irAEs caused by systemic anticancer treatment with ePRO follow-up	D3.2 Report on new knowledge on reduction of severe irAEs caused by systemic anticancer treatment with ePRO follow-up
T3.3 Analysing difference in survival	D3.3 Report on new knowledge on overall survival with ePRO
T3.4 Analysing HRQoL in ePRO patients related to irAE, progression of disease and death.	D3.4 Report on new knowledge on HRQoL in the ePRO study group
T3.5 Write article about findings	T3.5 Published article

4.3 Sample size estimation and power analysis

WP1 is a diagnostic study assessing whether the new NCAF oncology can be clinically useful as a screening tool for irAEs in cancer care. Sample size estimation is based on data from a metanalyses by Magee et al indicating that 16.6 percent of cancer patients experience severe irAEs (13). To achieve a minimum power of 80 % a sample size of 535 subjects will be required in order to detect a change in sensitivity from 0.80 to 0.90, based on a target significance level of 0.05 (actual $p=0.040$). Our proposed random sample of 600 patients receiving immunotherapy treatment from 2021-2023 should be more than adequate for the main objective of this study and should allow for possible subgroup analysis. Previous studies have shown that monitoring patients by ePROs reduces symptom burden (5,6), but no previous studies have investigated reduction in rates of AEs. WP2-3 should therefore be considered a pilot study and we estimate a reduction in severe AEs of 40 % to have a level of clinical importance. With an enrolment ratio of 2:1 and an alpha = 0.05 the project sample size needs approximately 300 patients monitored by the e-PROs and 600 patients followed up with standard care to reach a power of 80 percent. Today approximately 100 new patients yearly receive immunotherapy and are monitored by ePROs at NLSH and HSYK. With an expected increase in patients receiving immunotherapy our proposed enrolling 960 patients, where 320 are followed with ePRO, over a three

years period should be adequate for the main objective of the study. If insufficient participants are enrolled after three years, the inclusion period can be extended for additional 6-12 months.

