In 2013, Nordland Hospital Trust (NLSH) in collaboration with SAS Institute (SAS) developed a modified half automated version of the GTT method, called Nordic Clinical Analytics Framework (NCAF). Here machine learning (ML)-methods make it possible to find records with positive triggers which then are manually reviewed to verify if the triggers represent a true AE. Previous research on this half-automated technology have shown that it can efficiently replace manual identification, saves time and resources identifying AEs (8). From 2017 the NCAF method has been used by all hospital trusts in Northern Norway, however it has some drawbacks. Firstly, technology to fully automate identification of AEs is not yet developed. Secondly, NCAF lacks cancer-specific triggers to identify AEs related to systemic anticancer treatment such as chemotherapy, immunotherapy and other targets therapies. This makes it difficult to both identify, compare, and monitor AEs over time for cancer patients (1,9-12). To develop an automated identification of AEs we need to identify relevant triggers, before incorporating them into the NCAF technology. Recently a few studies have validated cancer-specific triggers, nevertheless, none of these validated oncology trigger tools uses automated identification of AEs (9-12). Furthermore, validated triggers to identify AEs related to modern anticancer treatments such as immunotherapy do not exist today. Immunotherapy introduces a different type of autoimmune AEs that can affect every organ system and causes 15 % severe AEs. To prevent development of severe irAEs it is important with early detection, since they can be reversed

[figure not shown]

Figure 1: E-PRO follow-up with Kaiku Health

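### The WP1 sample size of 535 fits a 20% rate of severe irAEs, not the stated 16.6%; the planned 600 patients give about 70–76% power, not at least 80%

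*Protocol*

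**What the plan says.** Section 4.3 of the Protocol treats WP1 as a diagnostic study of the new trigger tool. It takes its event rate from a meta-analysis "indicating that 16.6 percent of cancer patients experience severe irAEs". From that it concludes that "a sample size of 535 subjects will be required in order to detect a change in sensitivity from 0.80 to 0.90", for a minimum power of 80%, "based on a target significance level of 0.05" and an actual level of 0.040. It then says that the planned 600 patients "should be more than adequate for the main objective of this study and should allow for possible subgroup analysis".

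Section 4.4 adds that tests are two-sided at 5% and that confidence intervals for sensitivity use the Wilson score method. The background text before section 1.1 gives a second, slightly lower rate: immunotherapy "causes 15 % severe AEs". A rate of 20% is not given anywhere.

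**The concern.** The stated inputs do not lead to the stated total. Patients without a severe irAE contribute nothing to sensitivity, so the total depends directly on the assumed event rate. If 535 was worked out at a higher rate than the one cited, both the requirement and the apparent margin (600 against 535) are wrong.

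This is the only sample-size justification for WP1, which carries hypothesis H1 and objective O1. The tool validated there is then used to measure irAEs in WP2. As written, a reader would believe that the validation has at least 80% power with room to spare.

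**Working it through.** **Inputs.** From section 4.3: sensitivity 0.80 under the null and 0.90 under the alternative; power at least 80%; target alpha 0.05, actual 0.040; severe irAE rate 16.6%; required total 535; planned total 600. From section 4.4: two-sided testing. From the background text: alternative rate 15%.

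**Method.** One-sample test of a proportion among event patients. Total N = event patients / event rate.

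**Step 1: reproduce 535.** Two-sided exact binomial test with at most 0.025 in each tail:

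- The smallest number of event patients with at least 80% power is 107. The upper rejection region is 94 or more detected; power is 81.9% and actual alpha is 0.0402.
- The actual alpha agrees with the protocol's 0.040.
- 107 / 0.20 = 535 exactly.

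The protocol's total and its actual alpha are both recovered, but only with a rate of 20%.

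**Step 2: use the stated rate.** 107 / 0.166 = 644.6, so 645 patients. This is 645/535 = 1.206, or 20.6% more than stated. The normal approximation, [(1.96 × √(0.80 × 0.20) + 0.842 × √(0.90 × 0.10)) / 0.10]², gives 107.4, hence 108 event patients and 108 / 0.166 = 651.

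**Step 3: could another method give 535 at 16.6%?**

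| Method | Total at 16.6% |
|---|---|
| Two-sided exact | 645 |
| Two-sided normal | 651 |
| Two-sided, continuity-corrected | 706–707 |
| Two-sided arcsine | about 587 |
| One-sided exact (smallest n = 82) | 494 |
| One-sided normal | 500 |
| One-sided, continuity-corrected | 558 |
| Two-sample comparison | 946 or more |

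None is within 3% of 535.

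**Step 4: two-sided power actually available.**

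| Patients | Rate | Expected events | Exact power near that count | Exact, averaged over random count | Normal approximation |
|---|---|---|---|---|---|
| 535 | 16.6% | 88.8 | 73.7% (88), 72.5% (89) | 68.8% | 70.1% |
| 600 | 16.6% | 99.6 | 71.5% (99), 70.3% (100) | 74.6% | 76.2% |
| 600 | 15% | 90.0 | 71.3% (90) | 69.5% | 70.9% |
| 600 | 20% | 120.0 | 85.6% (120) | 83.5% | 85.0% |

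Only the 20% row clears 80%.

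**Step 5: precision.** With 90 of 100 events detected, the Wilson 95% interval for sensitivity is 0.826 to 0.945.

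**The case against.** Five points can be made for the plan.

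- **Sidedness.** Section 4.3 does not say whether the test is one- or two-sided. With a one-sided 5% test, 600 patients would give 81.2% power at 99 events, 87.6% at 100 and 84.2% on average, which is adequate. This does not explain 535, however. The smallest one-sided exact requirement is 82 events (494 patients), and the 88 or 89 events expected in 535 patients have a one-sided actual alpha of 0.046 or 0.042, not 0.040. Section 4.4 also specifies two-sided tests.
- **Discreteness.** Exact power moves in a sawtooth: 70.3% at 100 events is a trough, and 101 events give 79.2%. This stands. Since the event count is random, the averaged 74.6% describes the study better than any single count. It is still below 80%.
- **The Wilson score method.** Inverting the score interval gives 80.2% power at exactly 100 events, but with an actual type I error of 0.0595. At 99 events it gives 71.5%, and averaged over the event count 76.2%. It does not reach the target either.
- **Target condition.** H1 and O1 concern irAEs in general, and irAEs of any grade would be more frequent. The protocol gives no any-grade rate, and section 4.3 explicitly builds on severe irAEs. If any grade was meant, the section still needs correcting.
- **Consequence.** WP1 mainly reports estimates with confidence intervals, which remain valid with about 100 events, and exploratory subgroup estimates need no 80% power. This is fair. It limits the harm to the power claim and the assurance attached to it, but does not make those statements correct.

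**Conclusion.** The point holds. The total of 535 corresponds to a 20% rate of severe irAEs; the stated 16.6% requires 645. That 20% was used is an inference, but a strong one, because the total and the actual alpha both match. The mismatch itself needs no inference: the stated inputs do not produce 535 under any method tried.

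With 600 patients, power for 0.80 against 0.90 is about 70–76%, a shortfall of roughly 4 to 10 percentage points, with 74.6% the best single exact figure. At the 15% rate in the background text it is about 70–71%. These figures assume a two-sided 5% test, severe irAEs as the target condition, and all 600 patients used for the sensitivity estimate. Section 4.3 makes no allowance for dividing the 600 into development and validation sets; any such split would lower power further. Since the full sample misses the target, nothing in the calculation supports the subgroup assurance.

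**What to change.** Correct section 4.3 so that the rate, the total and the power agree:

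1. State the event rate used and that the test is two-sided.
2. Replace the requirement with wording such as: *at a severe irAE rate of 16.6%, 107 event patients, or about 645 patients, are needed; the planned 600 are expected to give about 100 event patients and about 70–76% power for sensitivity 0.80 against 0.90.* Note that 645 fixes the event count at its expected value; averaged over the random count, exact power at 645 is 78.1%.
3. Alternatively, restate the WP1 aim as precision: with sensitivity 0.90 in 100 event patients, the Wilson 95% interval runs from about 0.83 to 0.94.
4. Remove the statement that 600 exceeds what is needed, and remove the subgroup assurance or label any subgroup analysis as exploratory.

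If a rate of 20% was intended, cite a source for it and reconcile it with the 16.6% and 15% already in the document.

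The cost is a change of wording in one section and a less favourable power figure. No extra patients are required unless the sponsor chooses to restore 80% power.

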4.4 Statistical analysis

Poisson regressions in Generalized linear models will be applied to compare rates of irAEs, severity level and categories of types of irAEs between the different samples. Poisson regression was selected as it accounts for variation of number of cases and length of stay. Adjustments of demographical variables will be done by including these as covariates. When evaluating the performance of the automatic oncology trigger tool, a retrospective physician lead review of the EHR will be set as gold standard. To evaluate the validity of the automatic oncology trigger tool we will calculate sensitivity, specificity and positive predictive value (PPV) with their respective 95 % confidence intervals (CI). The CI for sensitivity, PPV and specificity will be calculated using the Wilson score method and two-sided tests with a significance level set at 5 %. F1-score and area under the curve (AUC-ROC) are other performance metrics that will be used. The Kaplan-Meier estimate will be used to calculate overall survival between the ePRO and the standard of care groups in WP3.

5 Progress plan and overview of activities

The PhD will be carried out over 45 months from April 2023 – February 2027. The candidate will combine 80 % research with 20 % clinical work as an oncologist at NLSH. The PhD candidate is a member of the Cancer Research Group at NLSH and apply for enrolment at the PhD-program at UIT the Arctic University of Norway. Data are already routinely collected from EHR at the three hospital trusts. Data collection for all three WPs and record reviewing of patient record for all WPs have already been started in 2021 as part of a quality improvement and other research projects. Figure 3 shows an overview of milestones, assigned tasks and roles of the project.

[figure not shown]

Figure 3 Overview project plan

6 Feasibility within the time frame

The Patient Safety Unit at NLSH have had two previous PhD projects evolving the automatic GTT-method and identifying AEs in cancer patients (1, 8). Knowledge and technology from this previous research on developing automatic measures are valuable and will be reused. The technology is already in use in Helse Nord, and new algorithms for the NCAF Oncology method will be developed by SAS Institute, Datavarehuset Helse Nord and technical personnel from NLSH, with separate external funding. Research related to validation and clinical impact is part of the PhD project. The project investigator and the PhD-candidate are both in clinical work at the Department of Cancer in NLSH and since 2020 responsible for developing and implementing the ePRO follow-up of cancer patients. As a result, some data is already available from the EHR and can easily be collected and analysed as discussed in section 5. The research will be linked to research groups both at NLSH and SHARE (Senter for kvalitet og sikkerhet i helsetjenesten) at the University of Stavanger (UIS), contributing with their broad experiences especially within healthcare research, patient safety and clinical oncology. Altogether the extended project group represent four out of five trusts in Helse Nord from both clinical and service departments with a broad national and international experience in relevant research and clinical oncology. We therefore argue that the feasibility of this research project is good.

7 Dissemination and publication plan

Findings will be disseminated in the academic field at national and international scientific conferences in cancer care, patient safety and technological development. The candidate and supervisors will disseminate the knowledge in teaching of medical students and healthcare personnel in Norway to enhance the knowledge of patient safety in cancer care. Offering our main results to media, patient organisations and the general public as articles, presentations, pod-, videocasts and blogs in social media as Twitter and Instagram will also be of high priority. The PhD-thesis will include three scientific papers published in open-source peer-review journals, with preliminary headings;

WP1: “Automated identification of irAEs in cancer care”

WP2: “Does ePRO follow-up reduce incidence of irAEs in cancer care?”

WP3:” Immunotherapy ePRO follow-up as standard of care in oncology – what difference does it make for the patients?”

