As the first hospital in Norway, the Cancer Department at NLSH implemented ePRO follow-up as standard of care for all patients receiving immunotherapy from June 2021 by using Kaiku Health. The immunotherapy module is based upon reported irAEs in clinical trials of immunotherapy (15-17). Kaiku health is a web-based program for smartphones, I-pads and home computers, and by using ML algorithms the software screen, grade and alert for potential harm. Based on received treatment each patient gets a personalised follow-up symptom- and QoL-questionnaire (the European Organisation of Research and Treatment of Cancer, EORTC, recommended QoL-module called QLQ C-30(18)) sent out regularly. Filled-out questionnaires are submitted digitally to the Cancer Department which is able to see in real-time the patient's status, and directly identify possible symptoms. This makes it easier to respond immediately to potentially serious irAEs and prevent further impairment of the patient. At the same time as the health care professionals are alerted, the patient gets information on his/her own device about how they should react and what to do, and how their symptoms have evolved over time. Figure 1 illustrates how ePRO follow-up with Kaiku Health works in clinical practice.

From analysing the current methods and technologies used to monitor AEs caused by anticancer treatment, we intend in work package (WP) 1 to develop and validate a fully automated cancer-specific trigger tool to identify irAEs occurring in both hospitalised and outpatient clinical practice, called NCAF Oncology. In WP 2 we will study how the NCAF Oncology works in clinical care, and compare the incidence and development of irAEs between cancer patients followed by ePRO compared to standard of care. In WP3 we investigate how QoL in cancer patients evolves under immunotherapy treatment with follow-up by ePRO, and also compare overall survival between standard and ePRO follow-up.

with timely intervention (13,14). Thirdly, NCAF only analyses hospitalised patients while most cancer patients receive ambulatory treatment, so monitoring AEs in an outpatient setting is essential to map the full extent of AEs.

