1.1 Expected benefits

By developing novel technology relevant in clinical practice our ambitions are to develop and validate the first fully automated NCAF Oncology method to monitor irAEs specific to modern immunotherapy anticancer treatment both in hospitalised and outpatient settings, with the future purpose to measure and mitigate irAEs with use of less resources. The key **academic impact** is validated technological methods to monitor irAEs from systemic anticancer treatment that can be directly implemented in everyday clinical practice. Development of a fully automated NCAF Oncology can be used to develop similar technological methods to identify AEs in other medical specialties. Improvement of the NCAF allows further research on prospective warning signals and clinical support integrated in the electronic health record (EHR) to mitigate other AEs in cancer care. The use of ePROs and QoL-score provides personalized follow-up to the patients. It also gives healthcare professionals the opportunity to focus on the patient`s perspective at the same time as they can mitigate and prevent harm before it results in a severe irAE. Importantly, the patients are proactive in their own patient journey with more knowledge about their own symptoms and how to react on them. This encourages empowerment and safety to the patient and their family, and has proved to reduce symptoms such as pain, depression and fatigue and increase patient`s QoL (6). It could also decrease the need for emergency admissions or unplanned visits/ phone calls at the outpatient clinic (5,6,15), which can be a burden to the patient, their family and the healthcare system. Knowledge about real time follow up and irAEs can be clinically relevant to better inform patients before starting new treatments. It may also provide information about when to end potentially harmful and high cost treatment, as alerted symptoms and/or decreasing QoL can signal toxicity or progressive disease (5,6,16,17).

2 The student`s contributions into the project

The PhD student will be responsible for data collection, analysis and writing of all articles in WP1-3. For detailed plan of candidate`s contributions see assigned tasks in project plan, section 5 *Project plan and overview of activities*.

3 Overall aim and hypotheses

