3.2 Hypotheses and research questions

We have identified the following hypotheses (H):

H1: We predict that the new developed NCAF Oncology can identify rates, type and severity of irAEs with high sensitivity and of relevance in clinical practice.

H2: By implementing ePRO as standard follow-up for cancer patients we predict that we can reduce the incidence of severe irAEs.

H3: By implementing ePRO as standard follow-up for cancer patients we predict that we can increase HRQoL and overall survival.

4 Materials and methods

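### Section 4.4 names length of stay as the only time quantity for the irAE rate model: an inpatient measure that ePRO may change and that fits neither H2 nor the WP2 sizing

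*Protocol*

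**What the plan says.** Section 4.4 specifies the model: "Poisson regressions in Generalized linear models will be applied to compare rates of irAEs, severity level and categories of types of irAEs". It then justifies the choice: "Poisson regression was selected as it accounts for variation of number of cases and length of stay". The only adjustment described is demographic: "Adjustments of demographical variables will be done by including these as covariates". The section names no follow-up time, time on treatment, person-time or observation window for irAEs.

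Other parts of the protocol bear on whether that time basis fits:

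- The introduction lists as a drawback of the existing tool that "NCAF only analyses hospitalised patients while most cancer patients receive ambulatory treatment". The new tool is meant to "identify irAEs occurring in both hospitalised and outpatient clinical practice".
- H2 in section 3.2 reads: "By implementing ePRO as standard follow-up for cancer patients we predict that we can reduce the incidence of severe irAEs".
- Section 4.3 sizes WP2-3 from 16.6% of patients with a severe irAE, a 40% reduction, a 2:1 ratio and alpha 0.05. It arrives at about 300 ePRO and 600 standard-care patients for 80% power.
- Section 1.1 says of ePRO: "It could also decrease the need for emergency admissions or unplanned visits/ phone calls at the outpatient clinic". The introduction also reports earlier chemotherapy studies in which ePRO follow-up could lower acute admissions.

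**The concern.** A comparison of rates needs a measure of time at risk. A patient on immunotherapy is at risk of an irAE from the first dose, in hospital or at home. Length of stay measures only days in hospital. It suits a trigger method that reviews admissions, which is the restriction this project sets out to remove.

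Three things are at stake. First, outpatient irAEs would be counted in the numerator without any matching exposure. Second, the protocol expects ePRO to affect admissions, so the quantity used to standardise the comparison may move with the intervention being compared. Third, a rate per inpatient day is a different quantity from the per-patient risk on which section 4.3 rests. The model as described would therefore not estimate the effect the study was sized to detect.

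**Working it through.** **1. What the sizing is based on.** Inputs from section 4.3: control proportion p1 = 0.166; a 40% relative reduction gives p2 = 0.6 × 0.166 = 0.0996; control:ePRO = 2:1; alpha 0.05, taken as two-sided; power 0.80.

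- Arcsine formula: h = 2·asin(√0.166) − 2·asin(√0.0996) ≈ 0.197. Control n = 3 × (1.960 + 0.842)² / h² ≈ 606, so ePRO n ≈ 303. Power at 600 + 300 is 79.6%.
- Pooled normal approximation: 630 + 315. Power is 78.0% at 600 + 300 and 80.7% at the planned 640 + 320.
- Unpooled normal approximation: 566 + 283. Power is 82.3% at 600 + 300.

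The stated 300 + 600 is thus reproduced by a comparison of per-patient proportions. Length of stay plays no part in it.

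**2. If length of stay is the offset.** The model then estimates events per inpatient day:

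rate ratio per inpatient day = per-patient rate ratio ÷ ratio of mean inpatient days (ePRO / standard care).

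The documents give no size for an effect of ePRO on inpatient days, so the reductions below are assumptions.

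| Assumed cut in inpatient days | True ratio 1.00 becomes | True ratio 0.60 becomes |
|---|---|---|
| 10% | 1/0.9 = 1.11 | 0.60/0.9 = 0.67 |
| 20% | 1/0.8 = 1.25 | 0.60/0.8 = 0.75 |
| 30% | 1/0.7 = 1.43 | 0.60/0.7 = 0.86 |
| 40% | 1/0.6 = 1.67 | 0.60/0.6 = 1.00 |

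At an assumed 40% cut, the whole targeted effect disappears.

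A patient never admitted has zero length of stay, and log(0) is undefined, so that patient cannot enter the model. The share never admitted is not given. If it were between 50% and 80% (assumed), 450 to 720 of 900 patients would be affected.

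**3. If length of stay is a covariate.** The offset problem and the figures in step 2 do not arise. The model would, however, adjust for a variable that ePRO may change, which can remove or distort part of the effect of interest. It would also have no term for time at risk.

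**4. What a person-time Poisson model would do to power.** Treat the two proportions as event rates over equal person-time, with log rate ratio ln(0.60) = −0.511.

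- At 600 + 300: variance = 1/(600 × 0.166) + 1/(300 × 0.0996) = 1/99.6 + 1/29.88 = 0.0435, SE = 0.209. Power = Φ(0.511/0.209 − 1.96) ≈ 69%.
- At 640 + 320: variance = 1/106.24 + 1/31.87 = 0.0408, SE = 0.202. Power ≈ 72%.

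Correcting the time basis while keeping a plain Poisson rate ratio as the main test would therefore not deliver the stated 80%.

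**The case against.** The strongest reply is that section 4.4 gives a rationale and not a model equation. The words offset, exposure and denominator do not appear, and a statistical analysis plan that is not shown here may define person-time. This stands in part: the offset is an inference, and the rate ratios of 1.25 and 0.75 depend on it. It does not remove the point. Length of stay is the stated reason for choosing the model and the only time quantity attached to it, and it is unsuitable as offset or covariate. A later plan that used person-time would have to replace that rationale.

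A reader might go further in three ways that the documents do not support.

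- *That most patients have zero exposure.* The introduction says most cancer patients are treated as outpatients. It does not say that they are never admitted during follow-up, and no share is given.
- *That the cohorts have unequal follow-up.* The calendar years given for the cohorts in section 4.2 are years of treatment or inclusion. No end of observation is stated for either cohort, so no imbalance can be calculated.
- *That plain Poisson gives intervals that are too narrow.* The protocol offers no information on the spread of irAE counts. For a severe irAE counted once per patient, variance/mean is about 1 − 0.166 = 0.83, which makes plain Poisson conservative.

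It is also fair to note that section 4.3 describes WP2-3 as a pilot, and that the protocol says only that ePRO may reduce admissions, with no figure for inpatient days.

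**Conclusion.** The point holds in a limited form. Section 4.4 rests its irAE rate model on a time quantity that conflicts with outpatient capture, with H2 and with the per-patient sizing in section 4.3, and that ePRO may itself alter. That conflict follows from the text alone.

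The size of any distortion cannot be determined from the documents. The illustrative shifts (1.00 to 1.25 and 0.60 to 0.75 at a 20% cut in inpatient days) rest on two assumptions: that length of stay enters as the offset, and that ePRO shortens total stay by that amount. The loss of never-admitted patients also requires the offset reading. Under the covariate reading, what remains is adjustment for a variable affected by ePRO and the absence of time at risk. Because this model provides the WP2 comparison that answers H2, the wording should be settled before that comparison is run.

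**What to change.** In section 4.4, remove length of stay as the rationale and time basis. Define person-time at risk as running from the first immunotherapy dose to the earliest of death, data cut, or the end of an observation window identical in both cohorts. Fit the log-link Poisson model with log person-time as offset and robust (sandwich) standard errors.

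For H2, make any severe irAE per patient within that window the main comparison, and keep the person-time rate model for all irAEs, types and severity levels. State in section 4.3 that the 80% power refers to the comparison of per-patient proportions.

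The cost is about one paragraph in section 4.4 and one sentence in section 4.3. The start-of-treatment and death dates needed should come from the same health record. Intervals may widen slightly with robust standard errors. If the team prefers a plain Poisson rate ratio as the main test, the sample size has to be reworked, since power would be about 69% at 300 + 600 and 72% at 320 + 640.
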